10.4.3 ANALYSIS OF THE SECONDARY ENDPOINT(S)

Analyses of Secondary Endpoints

Important secondary analyses will be conducted to compare means between the EVAC-PU-ETT and PVC-ETT treatments for quantitative outcomes (e.g., domain scores for the SF-36, cost, length of stay) using linear regression. For binary outcomes we will use logistic regression with robust (sandwich) standard error corrections. Comparison of survival outcomes between the EVAC-PU-ETT and PVC-ETT treatments (e.g., time to extubation, time to discharge from the ICU) will be performed using log rank test statistics. We will compare 6-month mortality between the two treatment groups using 6-month mortality estimates from the treatment groups' Kaplan-Meier curves. We will compare mean hospital length of stay, mean ventilator-free days and the mean SOFA scores between EVAC-PU-ETT and PVC-ETT using censored regression analysis. We will investigate whether the proportion of IVAC and VAEs differs between EVAC-PU-ETT and PVC-ETT among the subgroups of critically ill patients defined by gender and race. Formal comparisons between the treatment groups and patient subgroups will be investigated by fitting logistic regression models with robust variance estimates. We will perform omnibus tests of appropriately specified interaction terms between treatment assignment and patient subgroups. The mean and median overall per patient costs will be assessed for each randomized group, along with the clinical and hospital outcomes (consequences). We will investigate the mean difference in cost between the use of EVAC-PU-ETT and PVC-ETT. Cost will be defined in two ways: service-price and billable costs. We will formally test the difference in mean cost by using linear regression analysis with robust variance estimates. Inference on mean cost will be valid provided the sample size is moderately large (e.g.,

greater than 200 patients).⁷ We will use regression analysis to determine if there are greater/lesser benefits/risks in patient subgroups in the economic analysis. We will test for differences in median costs using randomization tests. All hypothesis tests described above will be two-sided. Test results will be deemed statistically significant if the associated p-values of the tests are less than 5 percent.

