
occurring during the ICU stay from enrollment until ICU discharge. An IVAC event is defined by a 14-day period, starting on the day of onset of worsening oxygenation. For this study, we will use the CDC proposed tiered approach algorithm that encompasses ventilator associated conditions (VAC), infection related ventilator-associated complication (IVAC), and possible VAP.
 
Step 1: VAC (≥1 required):
 
 1) Daily min FiO_2 increase ≥ 0.20 (20 points) for ≥ 2 days - OR 2) Daily min PEEP increase $\geq 3 \text{ cm H}_2\text{O}$ for ≥ 2 days (after two days of stable or decreasing daily minimum values) 
Step 2: IVAC:
 
 1) Temperature $>38.0^\circ\text{C}$ OR $<36.0^\circ\text{C}$ - OR 2) White blood cell count $\geq 12,000$ or $\leq 4,000 \text{ cells/mm}^3$ - AND 3) A new antimicrobial agent is started and is continued for ≥ 4 days. 
Step 3: Possible VAP:
 
Criterion #1: Positive cultures of one of the following specimens collected within $+\/- 2$ days of onset of VAC, meeting quantitative or semi-quantitative thresholds, without requirement for purulent respiratory secretions: 1) Endotracheal aspirate; 2) Bronchoalveolar lavage; 3) Protected specimen brush; 4) Lung tissue - OR
 
Criterion #2: Purulent respiratory secretions AND a positive culture of one of the following specimens (qualitative culture, or quantitative/semi-quantitative culture without sufficient growth to meet Criterion #1): 1) Sputum; 2) Endotracheal aspirate; 3) Bronchoalveolar lavage; 4) Lung tissue; 5) Protected specimen brush.
 
Other secondary endpoints related to VAP
 
 1) Incidence of ventilator-associated events (VAEs); 2) Respiratory antimicrobial use; 3) VAP risk using a "clinical" definition for interpretation of the study findings in the context of previous literature where clinical definitions were used; 4) Occurrence of early- versus late-onset IVAC and time to first IVAC event. Early-onset IVAC is defined as IVAC occurring within four days of tracheal intubation while late-onset VAP is defined as VAP occurring 5 days or later. 
Additional secondary clinical endpoints
 
 1) 28-day ventilator-free days; 2) Daily Sequential Organ Failure Assessment (SOFA) score; 3) Length of ICU and hospital stay; 4) In-hospital and 6-month mortality comparison between the two groups.

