VAP bundles and concomitant treatments that affect VAP: 1) Semi-recumbent position by capturing head of bed position (% of time >30° as automatically recorded by electronic beds); 2) stress ulcer prophylaxis, enteral calorie intake; 3) performance of oral hygiene, 4) use of neuromuscular blocking agents; 5) documentation of cuff pressure and application of subglottic suctioning; 6) Daily sedation vacation and spontaneous breathing trial (SBT).

VAP Treatment: Initial antimicrobial therapy is directed by hospital-wide guidelines. Use of respiratory antimicrobials and their duration will be collected.

During the ICU stay we will also collect the daily SOFA. As a summary measure, we will compute the mean of the daily score during the ICU stay.

Hospital stay variables: After discharge from the ICU, patients will be followed to obtain information on safety, disposition and antimicrobial treatment for VAP.

6-month follow-up: All patients will be followed-up six months after randomization with a structured in-person interview to screen for the presence of and assess airway symptoms or persistent sequelae of laryngeal dysfunction (Appendix II).¹⁰⁶ Any need for consultation of a specialist for airway complaints will be recorded and information abstracted from the medical record if appropriate. The clinical medical records release form collected at the time of informed consent will allow access to the subject's outside medical record for data related to the breathing problem. Quality of life will be also assessed, as measured by the physical component summary and the mental component summary of the Medical

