If the LAR is told about the research study and the subject's condition improves, the subject will also be informed about the research as soon as is feasible. The LAR, or subject will be given the opportunity to object to the study and refuse participation or withdraw from the study at any time without penalty or loss of benefits to which the subject is otherwise entitled. If the subject or LAR chooses to withdraw from the study after randomization, the study team will discontinue data collection on the patient at that time but will retain the data collected up until the time of withdrawal.

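### Mean ventilator-free days are assigned to an undefined censored regression although the score is bounded rather than censored, and the method for hospital length of stay is ambiguous

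*Combined protocol and SAP*

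**What the plan says.** Section 10.4.3 assigns methods to the secondary outcomes in a single paragraph.

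- It first compares means of "quantitative outcomes (e.g., domain scores for the SF-36, cost, length of stay) using linear regression". The stay in this list is not identified as ICU or hospital stay.
- Its sentence on survival outcomes covers "time to extubation, time to discharge from the ICU) will be performed using log rank test statistics".
- It then states: "We will compare mean hospital length of stay, mean ventilator-free days and the mean SOFA scores between EVAC-PU-ETT and PVC-ETT using censored regression analysis".

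Section 4 lists "28-day ventilator-free days" and "Length of ICU and hospital stay" among the additional secondary endpoints. Section 9.1 defines the SOFA summary: "we will compute the mean of the daily score during the ICU stay". Section 11.1.1.2 says that after withdrawal "the study team will discontinue data collection on the patient at that time", while data already collected are kept.

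The document does not say what kind of censored regression is meant, where its limits lie or which events censor. It also does not say how in-hospital death enters length of stay, or how death is scored in ventilator-free days.

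**The concern.** The plan promises a comparison of mean ventilator-free days, but the model it names does not directly estimate one. A patient with no ventilator-free days has a known score of 0; nothing below 0 has been hidden. A Tobit model treats that 0 as a cut-off normal variable, and its treatment coefficient is the shift in that hypothetical variable. Read as days gained, the coefficient would misstate the effect. For the primary quality-of-life outcome, section 10.4.2 makes the regression coefficient equal to the difference in means; nothing similar is done here.

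Hospital length of stay has a separate problem. One sentence may assign it linear regression and another assigns it censored regression, with no rule on which result counts. An analyst could settle that after seeing the data. Section 3.3.2 names shorter ventilation and shorter stay as hoped-for benefits, so these results will be read.

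**Working it through.** **1. The plan's own figure.** The plan states no effect size or power for ventilator-free days, stay or SOFA. Its only figure for a comparison of means is for quality of life (section 10.2): 0.17 SD, 537 per arm, 80% power, two-sided 5%. Check: 0.17 × √(537/2) − 1.96 = 2.786 − 1.96 = 0.826, and Φ(0.826) = 79.5%. The figure reproduces, but it has no bearing on this point.

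**2. Inputs for ventilator-free days.** From the plan: a 28-day score, compared as a mean, by censored regression. Assumed, because the plan gives nothing: deaths score 0; days on the ventilator are log-normal with median 4 and log-SD 1; the score is 28 minus those days, floored at 0; the model is a Tobit with normal errors and a lower limit at 0.

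**3. True mean difference.** Under these inputs survivors average 21.8 ventilator-free days, so an arm's mean is (1 − mortality) × 21.8.

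- 30% v 27% dead: 0.73 × 21.8 − 0.70 × 21.8 = 0.03 × 21.8 = 0.65 days.
- 40% v 37% dead: also 0.03 × 21.8 = 0.65 days.

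**4. Tobit coefficient divided by mean difference, simulated data.**

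| Scenario | Ratio | Repeat run |
|---|---|---|
| 30% v 27% dead | 1.48 | 1.50 |
| 40% v 37% dead | 1.71 | 1.73 |
| 30% v 27% dead, plus 1 day less ventilation | 1.28 | 1.28 |
| Equal mortality, 1 day less ventilation | 1.11 | 1.08 |

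In the first two rows a true 0.65 days would appear as about 0.65 × 1.48 = 0.96 and 0.65 × 1.71 = 1.11. Theory agrees in size: with a normal latent variable the ratio is about 1/(1 − share at the limit), that is 1/0.70 = 1.43 for 30% at 0 and 1/0.60 = 1.67 for 40%.

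**5. Direction.** In eight other assumed scenarios (200,000 per arm) the ratio ran from 0.28 to 1.54 and was 1.00 in one. The lowest arose when treatment raised the share at 0 (30% to 33%) while shortening ventilation (median 4 to 3 days): mean difference 0.27, coefficient 0.08. The discrepancy is not always an exaggeration.

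**6. Hospital length of stay.** Where stay is genuinely cut short and censoring is non-informative, a normal-errors censored regression recovered the mean difference. Normal stay, 16% censored: true −1.00, coefficients −0.98 to −1.01. Skewed stay, 5% to 20% censored: true −1.47 to −1.56, coefficients −1.43 to −1.56.

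**7. Mean SOFA.** If no patient's mean lies at a limit, the censored likelihood is the ordinary normal likelihood, and the coefficient is exactly the ordinary mean difference. Only a pile-up at a limit would separate the two.

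**The case against.** The strongest reply is that the plan never specifies a Tobit at 0. It does not say that deaths score 0, nor that the raw coefficient will be reported; a mean difference on the observed scale can be derived from such a model. This stands. What the text itself shows is an unspecified model attached to a bounded score, and the ratios are conditional on the assumptions above.

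The test itself may also change little. In 300 simulated trials of 537 per arm the coefficient and the raw mean difference correlated at 0.99. Signal-to-noise was nearly the same in the two mortality-only scenarios (0.95 v 0.97 and 0.95 v 0.93), though lower for the Tobit with equal mortality (mean z 0.65 v 0.89). The issue is therefore mainly the size and meaning of the reported effect.

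A reader might infer two stronger points.

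- *That the coefficient is wrong for all three outcomes.* Steps 6 and 7 do not support this. Withdrawal gives a real reason to censor stay, and for mean SOFA no bias is shown.
- *That hospital stay is given two contradictory methods.* The linear-regression list names stay without qualification and only as an example, and section 4 has both ICU and hospital stay. The list could mean ICU stay alone. The text does not say so, which makes it ambiguous rather than a certain contradiction.

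**Conclusion.** The point holds for ventilator-free days: the named method does not directly estimate the named comparison. Under a Tobit at 0 with deaths scored 0, the coefficient is roughly 1.1 to 1.7 times the mean difference in the four main scenarios, and other assumed patterns can push it below 1. The model form, the death score and all distributions are assumptions.

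For hospital stay the finding is ambiguity about which method governs, together with undefined censoring. If death were treated as non-informative censoring, the model would extrapolate stay beyond death; the plan does not say whether it would. For mean SOFA, censored regression is superfluous.

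This is a minor point, confined to secondary endpoints.

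**What to change.** In section 10.4.3:

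1. Ventilator-free days: state how death is scored, and compare means by linear regression with robust standard errors, as the same section already plans for cost. If a censored model is kept, define it and report the mean difference on the observed scale.
2. Mean SOFA: use the same robust linear regression, or likewise report the observed-scale difference.
3. Length of stay: say whether the linear-regression entry means ICU stay, hospital stay or both, and name one method for hospital stay. Keep a censored method only for stays cut short by withdrawal, list the censoring events, and do not treat death as non-informative censoring.

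Deleting the censored-regression sentence outright would go too far. It is the only stated handling of truncated stays, and ordinary regression on the recorded days would count those stays as complete.

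The cost is SAP wording. Section 10.2 already provides for a formal addendum with rationale, and no new data or patients are needed.

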2 PROTOCOL SUMMARY

2.1 SYNOPSIS

Title: Randomized Trial of Endotracheal Tubes to Prevent Ventilator-Associated Pneumonia – Prevent 2 Study

Study Description: The study will be a Phase II randomized, controlled trial that will equally randomize 1,074 patients requiring emergency endotracheal intubation to receive either a polyurethane-cuffed endotracheal tube equipped with continuous aspiration of subglottic secretions designed to prevent ventilator-associated pneumonia (EVAC-PU-ETT) or a conventional, polyvinylchloride-cuffed endotracheal tube (PVC-ETT). Using a pragmatic approach, we will determine if, by reducing the incidence of ventilator-associated pneumonia, the modified endotracheal tube (ETT) improves long-term quality of life and cognitive function, and if it is as safe as the conventional endotracheal tube, thus providing much needed evidence supporting decision-making.

Objectives: The primary objectives of the proposed trial are to compare the safety and effectiveness of EVAC-PU-ETT and PVC-ETT, initiated at the time of first emergency intubation in the ER or in-hospital. The specific aims are

as follows:

Primary Specific Aim: We will determine if long-term patient quality of life and cognitive function are better using EVAC-PU-ETT compared with PVC-ETT.

For the primary effectiveness endpoint, we will determine if the effect of EVAC-PU-ETT on quality of life (physical and mental component summary), as measured by the 36-item Short-Form General Health Survey, is better compared with PVC-ETT, at 6 months after randomization. An additional patient-centered endpoint will be the proportion of patients cognitively impaired, assessed by the National Alzheimer Coordinating Center's Uniform Data Set.

Secondary Specific Aims: We will determine if EVAC-PU-ETT is as safe as PVC-ETT. We will also determine if EVAC-PU-ETT reduces Infection Related Ventilator-Associated Complications (IVACs) and is more cost effective than PVC-ETT.

Aim 2. For our safety endpoint, we will evaluate the safety profile of EVAC-PU-ETT based on airway-related complications, compared with the PVC-ETT, at 6 months after randomization.

Aim 3. To determine if the EVAC-PU-ETT is effective in reducing the incidence of Center for Disease Control (CDC)-defined IVACs and Ventilator-Associated Events (VAEs) compared with PVC-ETT.

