Primary Endpoints	
The study primary endpoints will be measures of quality of life, and cognitive function at 6 months after randomization.
 
Quality of life. The patient interview will also include the evaluation of quality of life using the RAND version 1.0 of the Medical Outcomes Study 36-item Short-Form (SF-36) General Health Survey. This instrument includes eight sub-indices of the following types: vitality, physical functioning, bodily pain, general health perceptions, physical role functioning, emotional role functioning, social role functioning, and mental health. It also includes a single item that provides an indication of perceived change in health.
 
Cognitive function. At the six-month follow up, we will also assess cognitive function using a battery of tests assessing domains previously demonstrated to be potentially affected by periods of respiratory distress and validated in both normal aging and cognitively impaired populations. The core battery will consist of measures from the National Alzheimer Coordinating Center's Uniform Data Set (UDS): 1) Montreal cognitive assessment (MoCA), a global cognitive screen which has been shown to be much more sensitive than the Mini Mental Status Examination; 2) Craft Story Recall (an analogue to the Logical Memory subtest of the Wechsler Memory Scale), measuring immediate and delayed verbal contextual recall; 3) Benton Complex Figure test, which measures executive function and visuospatial ability, as well as

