Secondary Endpoints	
Safety. Safety endpoints include clinical measures intended to evaluate the direct effect of the device at the site of placement. To evaluate the effect of the ETT at the local level we will be assessing subjective and objective measures of laryngeal anatomy and function, in addition to any device-related adverse events. We will record: 1) airway complications at the time of ETT insertion; 2) the presence of cuff leak test prior to study ETT removal, as indicated by a difference between the inspiratory tidal volume (measured before cuff deflation) and the expiratory tidal volume (measured after cuff deflation) of at least 10% or >110 mL; 3) stridor immediately after extubation; 4) requirement for stridor treatment (racemic epinephrine, helium-oxygen gas mixture); or 5) reintubation within 24 hours due to upper airway complications such as stridor or obstruction. Long-term safety will be assessed by ascertaining the persistence of airway sequelae six months after randomization using a standardized questionnaire via in-person interview. Data collected include the presence of persistent throat discomfort or pain, residual hoarseness, change in voice, and dyspnea.
 
The main secondary clinical efficacy endpoint will be the incidence of CDC defined Infection-Related Ventilator-Associated Complications (IVAC)

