10.4.7 SUB-GROUP ANALYSES

We will investigate whether the proportion of IVAC and VAEs differs between EVAC-PU-ETT and PVC-ETT among the subgroups of critically ill patients defined by gender and race. Formal comparisons between the treatment groups and patient subgroups will be investigated by fitting logistic regression models with robust variance estimates. We will perform omnibus tests of appropriately specified interaction terms between treatment assignment and patient subgroups.

Also, we will use regression analysis to determine if there are greater/lesser benefits/risks in patient subgroups in the economic analysis.

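### Any secondary outcome, cost comparison or subgroup interaction can be called statistically significant at two-sided p<0.05; IVAC is ranked first, but the rank has no testing consequence

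*Combined protocol and SAP*

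**What the plan says.** Section 10.4.3 opens by giving the secondary analyses some weight: "Important secondary analyses will be conducted to compare means between the EVAC-PU-ETT and PVC-ETT treatments for quantitative outcomes". Its examples of quantitative outcomes are "domain scores for the SF-36, cost, length of stay". The same paragraph adds logistic regression for binary outcomes, log-rank tests, a comparison of 6-month mortality, censored regression for hospital stay, ventilator-free days and SOFA, tests of mean and median cost, and subgroup interactions by gender and race. It ends with "All hypothesis tests described above will be two-sided" and then the decision rule, "Test results will be deemed statistically significant if the associated p-values of the tests are less than 5 percent".

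Section 10.4.7 repeats the subgroup plan: "We will perform omnibus tests of appropriately specified interaction terms between treatment assignment and patient subgroups".

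Section 4 does set priorities. It introduces IVAC incidence as "The main secondary clinical efficacy endpoint", then lists other VAP-related endpoints, then further clinical endpoints. Section 2.1 words two of the secondary aims as questions to be settled: "We will also determine if EVAC-PU-ETT reduces Infection Related Ventilator-Associated Complications (IVACs) and is more cost effective than PVC-ETT".

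Sections 10.1 to 10.4.7 contain no testing order, alpha split, dependence on the primary result or exploratory label for secondary outcomes. The only adjustment described, in 10.4.2, is for the interim look at the safety endpoint.

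**The concern.** A rule for calling results significant needs a stated family, or a statement that the results are exploratory. Here the rule covers many outcomes and neither is given. If IVAC shows nothing, a p-value below 0.05 on all VAEs, clinically defined VAP, antimicrobial use, early or late IVAC, or time to first IVAC still qualifies as statistically significant under the plan's own words. So does one SF-36 domain, one cost comparison or one interaction.

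This matters because the central hypothesis in 10.1 includes superiority in reducing VAP, and every VAP-related endpoint is secondary. Evidence for that part of the hypothesis comes only from this group of tests. A report could say that the new tube significantly reduces some infection outcome, and the stated 5% would not be the error rate of a finding picked from the group.

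**Working it through.** **The plan's own figures.** The documents state no error rate for the secondary family, so there is none to reproduce. The nearest check is the alpha convention behind the power statements in 10.2 (two-sided 5%, 537 per arm).

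- Quality of life, 0.17 SD: Φ(0.17 × √(537/2) − 1.96) = Φ(2.786 − 1.960) = 79.5%, in line with the stated 80% up to rounding.
- Cognitive impairment, 0.40 against 0.31: 87.0%, consistent with at least 80%.

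So 5% in this plan means two-sided 5% for each test.

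**Counting the tests.** The documents give no count. This one is built from the text.

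| Source | Tests | Number |
|---|---|---|
| 10.4.3, with Section 4 ("This instrument includes eight sub-indices of the following types") | SF-36 domains | 8 |
| 10.4.3 | Cost: two definitions × mean and median | up to 4 |
| 10.4.3 | Time to extubation, time to ICU discharge, hospital stay, ventilator-free days | 4 |
| 10.4.3 | SOFA | 1 |
| 10.4.3 | 6-month mortality | 1 |
| 10.4.3 and 10.4.7 | Interactions: IVAC and VAE × gender and race | 4 |
| **Subtotal, 10.4.3** | | **22** |
| Section 4 | Infection outcomes: IVAC, VAE, antimicrobial use, clinical VAP, early/late IVAC, time to first IVAC | 6 |
| Section 4 | ICU length of stay, in-hospital mortality | 2 |
| **Total** | | **about 30** |

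Leaving out the four cost tests gives 30 − 4 = 26. Economic subgroups and the safety items in 10.4.4, for which that section specifies no test, are not counted.

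**Chance of at least one p<0.05 when every null is true.** For k independent tests the formula is 1 − 0.95^k:

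- k = 6: 1 − 0.7351 = 26.5%
- k = 22: 67.6%
- k = 26: 73.6%
- k = 30: 78.5%

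The tests are not independent and the documents give no correlations. The table treats the statistics as normal with one common correlation ρ, which is an assumption.

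| k | ρ = 0 | ρ = 0.3 | ρ = 0.5 | ρ = 0.7 | ρ = 0.8 |
|---|---|---|---|---|---|
| 22 | 68% | 57% | 44% | 30% | 23% |
| 26 | 74% | 62% | 48% | 32% | 24–25% |
| 30 | 79% | 66% | 51% | 34% | 26% |
| 6 (infection) | 26.5% | 24% | 21% | 16% | 14% |

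A more realistic structure has high correlation within a domain (0.5 to 0.9) and low correlation between domains (0.1 to 0.2). It gives 60% down to 44% for 22 tests and 70% down to 51% for 30.

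**False results favouring the new tube only.** Each test then contributes 2.5%, and the independent formula is 1 − 0.975^k. For the six infection outcomes: 1 − 0.8591 = 14% independent, 10% at ρ = 0.5 and 7% at ρ = 0.8. A single test carries 2.5%. For 26 tests the figures are 48%, 24% and 12%, although direction has no clear meaning for the interactions.

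**The case against.** The plan is not silent on priority. Section 4 has three tiers, with IVAC at the top. Clinically defined VAP is there so that findings can be compared with earlier literature, which is a supportive purpose. Section 7.3 places it and antimicrobial use among secondary analyses because some pneumonia is diagnosed clinically or without cultures. The wording in 2.1 that sounds confirmatory covers IVAC and cost-effectiveness, not SF-36 domains, SOFA or mortality. These are secondary endpoints of a Phase 2 trial, labelled as such, and leaving such endpoints unadjusted is acceptable when they are described as exploratory.

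Much of this stands, and it rules out three stronger readings.

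- A reader might infer that the plan has no hierarchy at all. It has a ranking of endpoints; what is missing is a testing hierarchy.
- A reader might infer that a false secondary claim is about as likely as not. That picks one value from a range of about 23% to 79%, requires every null to be true, and counts results in both directions.
- A reader might infer that VAP superiority can be claimed from any one of six infection tests. IVAC is named as the main one, and antimicrobial use is not VAP. Section 10 names no specific test for several of the six, so they fall under its generic methods.

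The count is also open to argument. ICU length of stay and time to ICU discharge nearly duplicate each other, and omnibus testing does not fix the interactions at four. Overlap by construction, such as IVAC being a subset of VAC, makes any single correlation a rough model.

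The objection does not remove the main point. Section 10.4.3 states a rule for calling results significant, applies it to all these tests, and never says that any of them are exploratory.

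**Conclusion.** The point holds as a gap between the ranking in Section 4 and the decision rule in 10.4.3. For roughly 22 to 30 tests the chance of at least one nominally significant result is 68% to 79% if independent, 44% to 51% at a common correlation of 0.5, and about 25% at 0.8. For the six infection outcomes it is about 14% to 26%, or 7% to 14% in favour of the new tube, against 2.5% for one test.

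These figures rest on every secondary null being true, on a count built from the text, and on assumed correlations. They show that the stated 5% is not the error rate of a claim selected from the set; they do not predict that a false claim will be made. A reader might infer that the primary conclusions are at risk. Nothing here bears on them. This is a cheap improvement to what may be claimed from secondary results.

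**What to change.** Replace the last sentence of 10.4.3 with the following, and refer to it from 10.4.7:

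> IVAC incidence is the single confirmatory secondary efficacy endpoint, tested at two-sided 5%. All other secondary efficacy, SF-36 domain and cost comparisons, and the subgroup interactions in 10.4.7, are exploratory; they are reported as estimates with 95% confidence intervals (nominal p-values if shown) and are not declared statistically significant. This does not apply to the safety non-inferiority test in 10.4.2.

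The last clause is needed because safety is listed among the secondary aims in 2.1 and 4 but is analysed as a primary endpoint in 10.1 and 10.4.2. A blanket label could demote it by accident.

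Do not make IVAC conditional on the primary result unless the plan first defines primary success across PCS, MCS and cognitive impairment. It does not do so now, so such a gate could not be applied. Without a gate, the change holds the formal secondary efficacy claim to 5% but does not control error jointly with the primary endpoints.

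No new data, visits or patients are needed. Section 10.2 already provides for a formal addendum with rationale, which should be in place before treatment codes are revealed. The cost is that secondary outcomes other than IVAC, including the planned formal cost comparison, can no longer be called statistically significant.
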